### 8.2.2. *Grade 3-4 Liver Toxicity*

The total number of patients with grade 3, grade 4 and grade 3-4 liver toxicity up to 12 months after treatment stop will be presented. Statistical tests of association, using logistic regression, adjusted for hospital and stratum (new/ retreatment case), between treatment and liver toxicity will be performed.

Due to the multiplicity of tests performed, the statistical tests of association between treatment and safety outcomes will not be interpreted as definite proof of more or less harm of any of the treatment but will be used as a screening tool. The use of a statistical tests will allow the exclusion of any observed difference which may be due to chance.

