The AEs and related treatments will be recorded in the patient file. An event is defined as an SAE when it meets one of the pre-defined outcomes.

Examples of an AE include:

1. Exacerbation of a chronic or intermittent pre-existing condition including either an increase in frequency and/or intensity of the condition.
2. New conditions detected or diagnosed after investigational product administration even though it may have been present prior to the start of the study.
3. Signs, symptoms, or the clinical sequelae of a suspected interaction.
4. Signs, symptoms, or the clinical sequelae of a suspected overdose of either investigational product or a concurrent medication (overdose per se should not be reported as an AE/SAE).

Examples of an AE do NOT include a/an:

1. Situations where an untoward medical occurrence did not occur (social and/or convenience admission to a hospital).
2. Anticipated day-to-day fluctuations of pre-existing chronic disease(s) or condition(s) present or detected at the start of the study that do not worsen.
3. Hospital admission for DOT (e.g. intensive phase of MDR treatment) or rapid DST
4. Pregnancy occurring during treatment, in absence of pregnancy complications

Serious Adverse Events

A Serious Adverse Event (SAE) is any adverse event/experience occurring at any study drug dose that results in any of the following outcomes:

- Death;
- Life threatening (subject at immediate risk of death);
- Requires in-patient hospitalization or prolongation of existing hospitalization;
- Results in congenital anomaly/birth defect;
- Results in a persistent or significant disability or incapacity;
- An important medical event that may not result in death, be life threatening, or require hospitalization may be considered an SAE when, based upon appropriate medical judgment, the event may jeopardize the subject and may require medical or surgical intervention to prevent one of the outcomes listed in this definition.

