8.1 Study hypotheses

This study is a pilot study to estimate the differences in the incidences in adverse treatment outcomes and excess toxicity. Consequently, the focus will be in describing event rates in each study arm and estimating the differences in event rates using odds-ratio's together with 95% confidence intervals (CIs) and not on formal hypothesis testing. P-values for comparisons of event rates (adverse treatment outcomes and safety endpoints) between intervention and control arms will be provided, but will need to be interpreted with care.

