8.3.3 Primary analysis

Counts and proportions (end 95% CI) of patients with any adverse treatment outcome, and by adverse treatment outcome category, will be presented. The confidence intervals for incidences will be estimated using Wilson's score method. Odds ratio's (ORs) and 95% CIs for the OR will be estimated from a logistic regression model with effects for arm (intervention vs control), hospital, and stratum (new/re-treatment case). The p-value for the test of no difference among arms will be presented. If the number of events is low a logistic regression model with an effect for hospital may be used instead of the full model proposed.

Similar analysis will be performed for the primary safety endpoint.

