8.4 Sample size and power

The sample size of two times 500 patients is a trade-off between precision and exposing an excessively high number of patients to potentially more toxic treatment. Power has not been taken into account, but if the results are favourable large scale cluster-randomized study will be designed to bring definitive proof.

The registered incidence of clinically apparent hepatitis from any cause during TB treatment is 1.5% for the study population. With the proposed sample size, an increase by at least 2% compared to the control arm will attain statistical significance ($p=0.047$).

With the standard (=control) regimens and definitions, about 2% failures and 2% relapses are currently notified by the DF project, but only 50% of those are culture-positive, and about half of the culture positive failures and relapses are rifampicin-resistant. Overall cure rate (new and retreatment cases together) is close to 90%, with 4% default and 4% deaths. Based on the data from 2010 about 20 cases with rifampicin resistance may be enrolled, 10 in each arm. We estimate that the more effective study regimen plus early detection of serious drug resistance rolled over to MDR-TB

treatment will prevent drug resistant failure and relapse, reduce rifampicin susceptible relapse to an estimated two third, and reduce death and default because of unrecognized rifampicin resistance to 80% of the control arm. This total estimated reduction of unfavourable outcome from 10% to 7% remains non-significant with the targeted enrolment of two times 500 cases. With 80% power and 95% confidence level, 2 x 1421 patients would have to be enrolled, which is not feasible and also difficult to justify. However, a slightly larger reduction of unfavourable outcome from 10% to 6.5% comparing two arms of 500 cases each would already result in a significant p-value. Additional evidence will be obtained studying *rpoB* mutations, initially (all smear-positives) and at time of failure or relapse (only in the few such cases expected). Absence of low-level resistance mutations only among patients with unfavourable outcome on the high-dose arm, while they were present among new cases in both arms, will be interpreted as additional evidence of effectiveness of the increased dosing.

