#### *Safety endpoint*

The primary safety endpoint will be the occurrence of any of the following:

- Serious Adverse Events
- Grade 3-4 Liver Toxicity following NIH common toxicity criteria (CTC), defined as transaminase increases to  $>225$  for men or  $>175$  for women/transgender (grade 3), or  $> 900$  for men or  $>700$  for women/transgender (grade 4)

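### SAP 8.2.2 says significance tests allow chance safety differences to be excluded, which a non-significant test cannot do; the SAP's 12-month safety window also does not match what the protocol collects

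*SAP*

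**What the plan says.** **Reading of the tests.** SAP 8.2.1 and 8.2.2 plan logistic-regression tests, adjusted for hospital and stratum, for any SAE, any drug-related SAE, the most common SAEs, and liver toxicity. SAP 8.2.2 then refers to the number of tests, calls them a screening tool, and says that they "will not be interpreted as definite proof of more or less harm". The closing sentence is: "The use of a statistical tests will allow the exclusion of any observed difference which may be due to chance". No significance level is given there.

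**Protocol approach.** Protocol 8.1 puts the focus on "estimating the differences in event rates using odds-ratio's together with 95% confidence intervals (CIs) and not on formal hypothesis testing" and adds that p-values, including those for safety endpoints, need care in interpretation. Protocol 8.3.3 sets out proportions with Wilson CIs and adjusted ORs with 95% CIs for efficacy, then states: "Similar analysis will be performed for the primary safety endpoint". The SAP (4.2, Safety endpoint) keeps the composite: "The primary safety endpoint will be the occurrence of any of the following", namely SAEs or grade 3-4 liver toxicity. SAP section 8 names no CI and gives no analysis of that composite.

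**Protocol figures.** Protocol 8.4: "The registered incidence of clinically apparent hepatitis from any cause during TB treatment is 1.5% for the study population". With 500 per arm, "an increase by at least 2% compared to the control arm will attain statistical significance", with p = 0.047 in brackets. The same section says that power was not taken into account.

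**Window.** SAP 8.2 summarises SAEs and liver toxicity up to 12 months after treatment stop. Protocol 7.1 registers SAEs from the start of treatment to its end. The schedule in protocol 5.1 marks no adverse-event collection at month +12 and places liver tests at enrolment, weeks 2 and 4, and month 2 (week 8 in the synopsis).

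**The concern.** A non-significant result says that the data are compatible with no difference. It does not say that they are incompatible with a harmful one. A rule that lets the analyst exclude whatever may be due to chance removes false signals and real ones alike, and it removes more real ones when events are few. The trial doubles the dose of one drug and was not sized on power, so imprecise safety contrasts are to be expected. The sentence also pulls against protocol 8.1, which asks for estimates with intervals.

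The window matters for a different reason. A table labelled as running to 12 months after treatment implies surveillance that the protocol does not provide after treatment ends.

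**Working it through.** **Inputs.** 500 per arm (protocol 4.3). Control rate 1.5% and a 2-point rise, that is 3.5% (protocol 8.4). The 1.5% is a rate for clinically apparent hepatitis; the documents give no rate for SAEs or for grade 3-4 liver toxicity, so what follows is an illustration. The two-sided 5% level is an assumption, consistent with protocol 8.4 treating p = 0.047 as significant.

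**Step 1: reproduce the protocol's figure.** 1.5% and 3.5% of 500 are 7.5 and 17.5, rounded to 8 and 18. Uncorrected Pearson test:

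- pooled proportion = 26/1000 = 0.026
- SE = √(0.026 × 0.974 × 2/500) = 0.01006
- z = (0.036 − 0.016)/0.01006 = 1.987, p = 0.0469

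This matches 0.047. Fisher's exact test on the same table gives 0.072.

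**Step 2: how often would a true rise of that size be non-significant?** Power = Σ Bin(a; 500, p1) × Bin(b; 500, p2) over all pairs (a, b) whose Pearson p-value is below the level.

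| True rates | Level | Power | Non-significant |
|---|---|---|---|
| 1.5% vs 3.5% | 5% | 0.538 | 46% |
| 1.5% vs 3.5% | 10% | 0.662 | 34% |
| 1.5% vs 3.5% | 1% | 0.288 | 71% |
| 1.5% vs 3.0% | 5% | 0.363 | 64% |
| 3% vs 5% (assumed) | 5% | 0.364 | 64% |

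These are unadjusted. Simulation of the planned logistic model (4000 trials per setting; assumed 3 or 8 equal sites, 10% retreatment, no site or stratum effect) gives 45% to 50% non-significant for 1.5% vs 3.5%, so adjustment does not change the picture.

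**Step 3: one case short of the benchmark, 8 vs 17.**

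- SE = √(0.025 × 0.975 × 2/500) = 0.00987; z = 0.018/0.00987 = 1.823; p = 0.068
- OR = (17/483)/(8/492) = 2.16
- SE(log OR) = √(1/8 + 1/17 + 1/492 + 1/483) = 0.434; 95% CI exp(0.772 ± 1.96 × 0.434) = 0.93 to 5.06
- risk difference +1.8 points, Newcombe 95% CI −0.18 to +3.93

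Read literally, the sentence would exclude this difference, although the interval reaches a rise of almost 4 points.

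**Step 4: the windows side by side.**

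| Item | SAP 8.2 | Protocol |
|---|---|---|
| SAEs | to 12 months after treatment stop | start to end of treatment (7.1) |
| Adverse-event collection at month +12 | implied | none marked (5.1) |
| Liver tests | to 12 months after treatment stop | scheduled to week 8/month 2; later results only if unscheduled |
| Deaths | to 12 months after treatment stop | may be learned of at the month +12 visit (5.3) |

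The mismatch is clear for SAEs and liver toxicity and only partial for deaths. Its effect on the proportions cannot be sized from the documents.

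**The case against.** The best defence is context. The sentence follows a reference to multiplicity and one that bars reading the tests as definite proof of more or less harm. It can be taken as a filter for chance positives among many SAE categories. It does not say that non-significance shows safety, and it suppresses no output, because counts by arm are presented whatever the p-value. The 46% also largely restates the low power that protocol 8.4 accepts openly.

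Much of this stands. It limits how far the sentence would mislead, and it means the SAP does contain a second, more cautious sentence of guidance. It does not make the rule correct: the caution concerns proof, while the closing sentence still licenses exclusion, and a filter with this error rate would drop real rises too.

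Three stronger readings are tempting and not supported.

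- *That non-significance would decide whether the larger study goes ahead.* The SAP introduction bases that decision partly on the absence of excess toxicity, but no document ties it to these p-values. A DSMB also reviews toxicity quarterly (protocol 7.2).
- *That the SAP contradicts the protocol on CIs and the composite.* It is silent. Protocol 8.3.3 still plans them, SAP 4.2 still defines the composite, and the planned logistic model can supply an OR and its CI. The tested any-SAE category is probably close to the composite, because transaminases above 5 ULN lead to referral for hospitalization and one SAE criterion is "Requires in-patient hospitalization or prolongation of existing hospitalization".
- *That the window loses or distorts events.* Twelve months is an upper bound, so nothing collected is lost.

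**Conclusion.** The closing sentence of SAP 8.2.2 is wrong as written and should be changed. With 500 per arm, a true rise from 1.5% to 3.5% is non-significant about 46% of the time in an unadjusted 5% test, with a range of 34% to 71% for levels from 10% to 1%. These figures rest on a hepatitis rate that is not the rate of either tested endpoint and on an assumed level, so they show the order of the problem and do not forecast this trial's result. The logical fault does not depend on them.

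The CIs and the composite analysis are a carry-over from the protocol and not a separate error. The window mismatch is real in the text, is secondary, and probably has a small effect, since little is collected after treatment. Its main consequence is a table label that claims more follow-up than was planned.

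**What to change.** 1. Delete the last sentence of SAP 8.2.2, or replace it with: *A non-significant test will not be taken as evidence of no difference; safety contrasts will be judged from their 95% CIs.*
2. In SAP section 8, carry over from protocol 8.1 and 8.3.3 the analysis of the primary safety composite: proportion by arm with Wilson CI, and OR with 95% CI from the planned logistic model. Give the same intervals for any SAE and for grade 3-4 liver toxicity.
3. Reconcile the safety window with the protocol. Set the main window to the protocol's collection period, and define treatment end for patients who restart a regimen or switch to the MDR regimen (for example, the end of the first assigned regimen). Include unscheduled on-treatment liver results and state that scheduled testing ended at week 8. List post-treatment deaths and events separately.
4. Optionally, because planned treatment of retreatment cases lasts 8 months in control and 6 in intervention, add a sensitivity comparison over the common first 6 months.

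The cost is SAP wording and one table for the composite. No new data, visits, patients or decision criterion are needed.
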